### **3.3. End of Trial**

The End of Trial is defined as either the date of 36 months from the last subject randomized date, or the date when all subjects discontinued from study treatment and no subject is available for survival follow-up, whichever is the later date.

The Sponsor may consider closing the trial when data supporting key endpoints and objectives of the study have been analyzed, and the availability of a roll-over or extension protocol exists into which any subjects who remain on study treatment may be consented and continue to receive access to study treatment. Such a protocol would be written for a compound that would not yet be commercially available.

**Figure 1: Overall Study Design**

Key: AML = acute myeloid leukemia; BSC = best supportive care; CCR = conventional care regimen; CR = morphologic complete remission; CRi = morphologic complete remission with incomplete neutrophil recovery; CRp = morphologic complete remission with incomplete platelet recovery; EOT = end of treatment; HSCT = hematopoietic stem cell transplantation; IDAC = intermediate-dose cytarabine; IDH2 = isocitrate dehydrogenase isoform 2; IV = intravenously; LDAC = low-dose cytarabine; PD = progressive disease; PO = orally; SC = subcutaneously.

\* Stratification factors: prior intensive therapy for AML (yes versus no), primary refractory (yes versus no), and prior allogeneic HSCT for AML (yes versus no).

## 4. STUDY POPULATION

### 4.1. Number of Subjects

Approximately 316 subjects 60 years or older with AML refractory to or relapsed after second- or third-line AML therapy and positive for an IDH2 mutation will be enrolled worldwide.

### 4.2. Inclusion Criteria

Subjects must satisfy the following criteria to be enrolled in the study:

1. Subject is  $\geq 60$  years of age at the time of signing the ICF
2. Subject has primary (ie, de novo) or secondary (progression of MDS or myeloproliferative neoplasms ([MPN], or therapy-related) AML according to WHO classification ([Appendix B](#))
3. Subject has received second- or third-line of AML therapy (see [Appendix G](#) for the definition of prior AML line; note that, for subjects having AML secondary to prior higher risk [Intermediate-2 or High risk according to the International Prognostic Scoring System] MDS treated with a hypomethylating agent [eg, azacitidine or decitabine], the hypomethylating therapy can be counted as a line if there is disease progression to AML during or shortly [eg, within 60 days] after the hypomethylating therapy.)
4. Subject has the following disease status:
  - a. Refractory to or relapsed after second- or third-line of intensive therapy for AML (eg, the “7 + 3” regimen):  
at least 5% leukemic blasts in bone marrow (the minimum number of treatment cycles of the intensive therapy is per the investigator’s discretion); or
  - b. Refractory to or relapsed after second- or third-line low-intensity AML therapy (eg, LDAC, azacitidine or decitabine):  
at least 5% leukemic blasts in bone marrow after at least 2 treatment cycles
5. Subject is eligible for and willing to receive the pre-selected CCR treatment option, according to the investigator’s assessment (Note: Subjects with degenerative and toxic encephalopathies, especially after the use of methotrexate or treatment with ionizing radiation, should not receive cytarabine.)
6. Subject has Eastern Cooperative Oncology Group (ECOG) performance status of 0, 1 or 2 ([Appendix D](#))
7. Subject has IDH2 gene mutations tested centrally (using the “investigational use only” PCR assay, Abbott RealTime IDH2) in samples of bone marrow aspirate **and** peripheral blood, and confirmed positive in bone marrow aspirate **and/or** peripheral blood. (Note: in the event that the central laboratory result is delayed and precludes acute clinical management of a subject who has confirmed IDH2 gene mutation by local evaluation, the subject may be eligible for randomization with approval by the Medical Monitor.)

8. Subject has adequate organ function defined as:
- Aspartate aminotransferase (AST)/serum glutamic oxaloacetic transaminase (SGOT) and alanine aminotransferase (ALT)/serum glutamic pyruvic transaminase (SGPT)  $\leq 3 \times$  upper limit of normal (ULN), unless considered due to leukemic organ involvement, following review by the Medical Monitor; and
  - Serum total bilirubin  $\leq 1.5 \times$  ULN, unless considered due to Gilbert's syndrome (eg, a gene mutation in UGT1A1) or leukemic organ involvement, following review by the Medical Monitor; and
  - Creatinine clearance  $> 30$  mL/min based on the Modification of Diet in Renal Disease (MDRD) glomerular filtration rate (GFR):  
$$\text{GFR (mL/min/1.73 m}^2\text{)} = 175 \times (\text{serum creatinine})^{-1.154} \times (\text{Age})^{-0.203} \times (0.742 \text{ if female}) \times (1.212 \text{ if African American})$$
9. Females of childbearing potential (FCBP)\* may participate, providing they meet the following conditions:
- Agree to practice true abstinence\*\* from sexual intercourse or to use highly effective contraceptive methods (eg, combined [containing estrogen and progestogen] or progestogen-only associated with inhibition of ovulation, oral, injectable, intravaginal, patch, or implantable hormonal contraceptive; bilateral tubal occlusion; intra-uterine device; intrauterine hormone-releasing system; or male partner sterilization [note that vasectomized partner is a highly effective birth control method provided that partner is the sole sexual partner of the FCBP trial participant and that the vasectomized partner has received medical assessment of the surgical success]) at screening and throughout the study, and for 4 months following the last study treatment (6 months following the last dose of cytarabine); and
  - Have a negative serum  $\beta$ -subunit of human chorionic gonadotropin ( $\beta$ -hCG) pregnancy test (sensitivity of at least 25 mIU/mL) at screening; and
  - Have a negative serum or urine (investigator's discretion under local regulations)  $\beta$ -hCG pregnancy test (sensitivity of at least 25 mIU/mL) within 72 hours prior to the start of study treatment in the Treatment Phase (note that the screening serum pregnancy test can be used as the test prior to the start of study treatment in the Treatment Phase if it is performed within the 72-hour timeframe).
10. Male subjects must agree to practice true abstinence\*\* from sexual intercourse or to the use of highly effective contraceptive methods (as described above) with non-pregnant

---

\* A female of childbearing potential is a sexually mature woman who 1) has not undergone a hysterectomy (the surgical removal of the uterus) or bilateral oophorectomy (the surgical removal of both ovaries) or 2) has not been naturally postmenopausal (amenorrhea following cancer therapy does not rule out childbearing potential) for at least 24 consecutive months (ie, has had menses at any time during the preceding 24 consecutive months).

\*\*True abstinence is only accepted as a method of contraception when it is the preferred and usual lifestyle of the subject. Periodic abstinence (calendar, symptothermal, post-ovulation methods), withdrawal (coitus interruptus), spermicides only, and lactational amenorrhoea method are not considered to be acceptable methods of contraception.

female partners of childbearing potential at screening and throughout the course of the study, and should avoid conception with their partners during the course of the study and for 4 months following the last study treatment (6 months following the last dose of cytarabine; 6 months following the last dose of azacitidine in Canada)

11. Subject must understand and voluntarily sign an ICF prior to any study-related assessments/procedures being conducted
12. Subject is willing and able to adhere to the study visit schedule and other protocol requirements

### 4.3. Exclusion Criteria

The presence of any of the following will exclude a subject from enrollment:

1. Subject is suspected or proven to have acute promyelocytic leukemia based on morphology, immunophenotype, molecular assay, or karyotype ([Appendix B](#))
2. Subject has AML secondary to chronic myelogenous leukemia (CML; [Appendix C](#))
3. Subject has received a targeted agent against an IDH2 mutation
4. Subject has received systemic anticancer therapy or radiotherapy < 14 days prior to the start of study treatment. Note that hydroxyurea is allowed prior to the start of study treatment for the control of leukocytosis (however, hydroxyurea should not be given within 72 hours prior to and after administration of azacitidine).
5. Subject has received non-cytotoxic or investigational agents < 14 days or 5 half-lives, whichever is longer, prior to the start of study treatment
6. Subject has undergone HSCT within 60 days prior to the start of study treatment, or on immunosuppressive therapy post HSCT at the time of screening, or with clinically significant graft-versus-host disease (GVHD). The use of a stable dose of oral steroid post-HSCT and/or topical steroids for ongoing skin GVHD is permitted.
7. Subject has persistent, clinically significant non-hematologic toxicities from prior therapies
8. Subject has or is suspected of having central nervous system (CNS) leukemia. Evaluation of cerebrospinal fluid is only required if CNS involvement by leukemia is suspected during screening.
9. Subject has active uncontrolled systemic fungal, bacterial, or viral infection (defined as ongoing signs/symptoms related to the infection without improvement despite appropriate antibiotics, antiviral therapy, and/or other treatment)
10. Subject has immediately life-threatening, severe complications of leukemia such as uncontrolled bleeding, pneumonia with hypoxia or shock, and/or disseminated intravascular coagulation
11. Subject has significant active cardiac disease within 6 months prior to the start of study treatment, including New York Heart Association (NYHA) class III or IV congestive heart failure ([Appendix E](#)); acute coronary syndrome (ACS); and/or stroke; or left

- ventricular ejection fraction (LVEF) < 40% by echocardiogram (ECHO) or multi-gated acquisition (MUGA) scan obtained within 28 days prior to the start of study treatment
12. Subject has prior history of malignancy, other than MDS, MPN or AML, unless the subject has been free of the disease for  $\geq 1$  year prior to the start of study treatment. However, subjects with the following history/concurrent conditions are allowed:
    - Basal or squamous cell carcinoma of the skin
    - Carcinoma in situ of the cervix
    - Carcinoma in situ of the breast
    - Incidental histologic finding of prostate cancer (T1a or T1b using the tumor, node, metastasis clinical staging system)
  13. Subject is known seropositive or active infection with human immunodeficiency virus (HIV), or active infection with hepatitis B virus (HBV) or hepatitis C virus (HCV)
  14. Subject is known to have dysphagia, short-gut syndrome, gastroparesis, or other conditions that limit the ingestion or gastrointestinal absorption of drugs administered orally
  15. Subject has uncontrolled hypertension (systolic blood pressure [BP] > 180 mmHg or diastolic BP > 100 mmHg)
  16. Subject is a pregnant or lactating female
  17. Subject has known or suspected to have hypersensitivity to any of the components of study treatment
  18. Subject is taking those medications (listed in Section 8.2) that are known to prolong QT interval unless the subject can be transferred to other medications at least 5 half-lives prior to the start of study treatment
  19. Subject has QTc interval (ie, Fridericia's correction [QTcF])  $\geq 450$  ms or other factors that increase the risk of QT prolongation or arrhythmic events (eg, heart failure, hypokalemia, family history of long QT interval syndrome) at screening
  20. Subject is taking the following sensitive CYP substrate medications that have a narrow therapeutic range are excluded from the study unless the subject can be transferred to other medications at least 5 half-lives prior to the start of study treatment: paclitaxel and docetaxel (CYP2C8), phenytoin (CYP2C9), S-mephenytoin (CYP2C19), thioridazine (CYP2D6), theophylline, and tizanidine (CYP1A2)
  21. Subject is taking the breast cancer resistance protein (BCRP) transporter-sensitive substrate rosuvastatin should be excluded from the study unless the subject can be transferred to other medications at least 5 half-lives prior to the start of study treatment
  22. Subject has any significant medical condition, laboratory abnormality, or psychiatric illness that would prevent the subject from participating in the study
  23. Subject has any condition including the presence of laboratory abnormalities, which places the subject at unacceptable risk if he/she were to participate in the study

24. Subject has any condition that confounds the ability to interpret data from the study

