d The subject should start study treatment (ie, Day 1 of Cycle 1) within 3 days after randomization.

e Subject should continue to be eligible for study entry prior to the start of study treatment on Day 1 of Cycle 1.

- f Cycle 1 only.
- g See Section 6.1 for details regarding collecting BMA, BMB, PBS and cytogenetics at screening for assessing AML disease status, collecting BMA and PB at screening for central testing IDH gene mutations [REDACTED]. In the event that the central laboratory result is delayed and precludes acute clinical management of a subject who has confirmed IDH2 gene mutation by local evaluation, the subject may be eligible for randomization with approval by the Medical Monitor.
- h All prior medications (prescription and non-prescription) taken and treatment procedures received from the 4-week period (ie, 28 days) prior to starting study treatment (including those prior to the start of study treatment on Day 1 of Cycle 1), and all prior anticancer therapies, regardless of discontinuation date of treatment.
- i Documentation of CCR treatment option selected by the investigator must occur prior to randomization.
- j Source documented only.
- k The BSA calculation is per the Dubois & Dubois formula:  $BSA (m^2) = \text{weight (kg)}^{0.425} \times \text{height (cm)}^{0.725} / 139.2$ . Where applicable, the dose should be calculated on Day 1 of each treatment cycle.
- l These assessments will be done locally.
- m The screening ECHO does not need to be repeated if a prior ECHO or multi-gated acquisition (MUGA) scan has been performed within 28 days prior to the start of study treatment.
- n Pregnancy test is required for all FCBPs (see Section 4.2 for the definition). Serum  $\beta$ -hCG pregnancy test (sensitivity of at least 25 mIU/mL) will be performed centrally at screening. For FCBP subjects, a local serum or urine (investigator's discretion under local regulations)  $\beta$ -hCG pregnancy test (sensitivity of at least 25 mIU/mL) is to be done within 72 hours prior to study treatment administration on Day 1 of every treatment cycle in the Treatment Phase and at the EOT visit. Negative results are required for study treatment administration.

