### **7.2.1. AG-221 Treatment**

Subjects randomized to the AG-221 treatment arm will receive continuous 28-day cycles of AG-221 100 mg PO QD for 28 days. In addition, subjects may receive BSC per standard institutional practice and as deemed necessary by the investigator. In order to optimally benefit from the AG-221 treatment, the investigator should aim to treat subjects for at least 6 cycles or as long as subjects continue to benefit from the treatment until the End of Trial. Subjects may be discontinued from the treatment for any of the reasons detailed in Section 11.1.

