### 8.2. Prohibited Concomitant Medications and Procedures

Systemic anti-cancer therapy (excluding hydroxyurea) is not permitted during the course of study treatment. Hydroxyurea is allowed after the start of study treatment for the control of leukocytosis and/or if subjects experience IDH Differentiation Syndrome during the course of study treatment.

If AML therapy other than the study-prescribed treatment is required for treatment of the subject's AML disease, the subject should be discontinued from study treatment.

The following therapies are not permitted during the course of azacitidine treatment:

- Oral retinoids (topical retinoids are permitted)

The following therapies are not permitted during the course of AG-221 treatment:

- Corticosteroids, with the exception of topical cutaneous, ophthalmic, nasal, and inhalational steroids. Note that short course steroid therapy will be permitted to treat co-morbidities such as IDH Differentiation Syndrome. The use of a stable dose of oral steroids post HSCT and/or topical steroids for ongoing skin GVHD is permitted.
- The following medications that are known to prolong QT interval: amiodarone, arsenic trioxide, astemizole, azithromycin, bepridil, chloroquine, chlorpromazine, cisapride, citalopram, clarithromycin, disopyramide, dofetilide, domperidone, droperidol, erythromycin, escitalopram, flecainide, halofantrine, haloperidol, ibutilide, levomethadyl, mesoridazine, methadone, moxifloxacin, pentamidine, pimozide, probucol, procainamide, quinidine, sevoflurane, sotalol, sparfloxacin, terfenadine, thioridazine, or vandetanib
- Sensitive CYP substrate medications that have a narrow therapeutic range: paclitaxel and docetaxel (CYP2C8), phenytoin (CYP2C9), S-mephenytoin (CYP2C19), thioridazine (CYP2D6), theophylline and tizanidine (CYP1A2)
- The BCRP transporter-sensitive substrate rosuvastatin

The following therapies are not permitted during the course of cytarabine treatment:

- 5-Fluorocytosine (the antifungal efficacy of 5-Fluorocytosine has been shown to be abolished during cytarabine therapy)
- Live or live-attenuated vaccines (Administration of these vaccines may result in serious or fatal infections. Killed or inactivated vaccines may be administered; however, the response to such vaccines may be diminished.)

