8.4.1. Prior/Concomitant/Follow-up Medications

All prior, concomitant and follow-up medications will be summarized in frequency tabulations (subject counts and percentages) and by World Health Organization ATC first level and PT. Listings will also be provided for general medications and concomitant QT prolonging medications. All tables described in this section will be produced on safety population.

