11.7. Electrocardiograms

Electrocardiogram (ECG) parameters include heart rate, PR interval, QRS duration, RR interval, QT, QTc Fridericia value (QTcF) and QTc Bazett value (QTcB). QTcB is not recorded in the CRF page and will be calculated in the following way: $QTcB = QT / \sqrt{RR}$.

Recorded values and of ECG parameters and change from baseline values will be summarized at each time point by treatment group.

In addition, at baseline and maximum post-baseline visits, the proportion of subjects having absolute QTcF and QTcB intervals of the following categories will be presented:

- ≤ 450 ms
- > 450 to ≤ 500 ms
- > 500 ms

At maximum post-baseline visits, the proportion of subjects who have an increase from baseline in QTcF and QTcB intervals of the following categories will be presented:

- ≤ 30 ms
- > 30 to ≤ 60 ms
- > 60 ms

The overall ECG interpretation will be summarized by presenting the shift from baseline to worst by treatment group and by cycle. The overall ECG interpretation will be displayed in cross-tabulations for each treatment.

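### QTc outlier tables take each subject's maximum over all ECGs, so the lower categories partly reflect time on treatment; QT-prolonging drugs are barred on treatment only under AG-221, and the SAP does not relate their use to QTc

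*Protocol*

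**What the plan says.** **Entry.** Exclusion criterion 18 (Protocol 4.3) applies to everyone: "Subject is taking those medications (listed in Section 8.2) that are known to prolong QT interval unless the subject can be transferred to other medications". The washout it requires is five half-lives before study treatment. Footnote e of Table 3 carries eligibility up to the first dose: "Subject should continue to be eligible for study entry prior to the start of study treatment on Day 1 of Cycle 1".

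**On treatment.** Protocol 8.2 puts the named drugs ("The following medications that are known to prolong QT interval: amiodarone, arsenic trioxide, astemizole, azithromycin" and others) under one heading: "The following therapies are not permitted during the course of AG-221 treatment". The list introduced by "The following therapies are not permitted during the course of cytarabine treatment" contains only 5-fluorocytosine and live vaccines. The azacitidine list contains only oral retinoids, and BSC has no list.

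**ECG schedule.** In both arms Table 3 schedules a 12-lead ECG at screening, on Days 1 and 15 of Cycles 1 and 2, on Day 1 of each later cycle and at EOT, with none in follow-up. For AG-221, Protocol 7.2.1 says "the investigator should aim to treat subjects for at least 6 cycles". No minimum number of cycles is stated for any CCR option.

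**Analysis.** SAP 11.7 says that "at baseline and maximum post-baseline visits, the proportion of subjects having absolute QTcF and QTcB intervals of the following categories will be presented", with cuts at 450 and 500 ms, and classifies the maximum increase at 30 and 60 ms. It sets no window and does not account for the number of ECGs. On concomitant drugs, SAP 8.4.1 plans frequency tables by preferred term and adds: "Listings will also be provided for general medications and concomitant QT prolonging medications".

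**The concern.** QT prolongation is the first adverse event of special interest in SAP 11.2, so readers will compare arms on the SAP 11.7 tables. Two features other than a drug effect can move that comparison.

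- A maximum over more ECGs tends to be larger by chance alone. If AG-221 subjects stay on treatment longer, they have more ECGs and more of them cross a low threshold.
- After Cycle 1 Day 1 the listed drugs remain barred only under AG-221. Any use in CCR could raise CCR values and narrow or reverse a difference.

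If AG-221 is the longer-treated arm, the two pull in opposite directions. The documents do not allow a net direction to be worked out.

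**Working it through.** The plan states no figure for this point, so there is none to reproduce.

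**1. Scheduled post-baseline ECGs (Table 3).** Cycle 1 Day 1 serves as baseline.

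- 1 cycle: C1D15 and EOT = 2.
- 2 cycles: C1D15, C2D1, C2D15 and EOT = 4.
- 6 cycles: the 4 above plus Day 1 of Cycles 3 to 6 = 8.

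**2. Chance of a maximum rise above a threshold t with no drug effect.** Assume one baseline ECG and k later ECGs, independent and normal around the subject's own mean with within-subject SD s. Then P = 1 − ∫ Φ(z + t/s)^k φ(z) dz. The values of s are assumptions; the documents give none. For t = 30 ms:

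| s (ms) | k = 2 | k = 4 | k = 8 |
|---|---|---|---|
| 8 | 0.8% | 1.4% | 2.5% |
| 10 | 3.1% | 5.5% | 9.0% |
| 12 | 6.9% | 11.5% | 17.8% |

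For t = 60 ms with k = 8, P is about 0.00005%, 0.009% and 0.15%. For an absolute value above 500 ms (assuming mean 415 ms, between-subject SD 15 ms, baseline below 450 ms), P is below 0.001% with 8 ECGs at all three SDs.

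**3. Treatment time varying within each arm.** This simulation had no drug effect, exponential treatment times, the same mean and between-subject SD, and 400,000 subjects per arm. Rates are longer v shorter arm:

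| Medians (assumed) | s (ms) | Above 450 ms | Rise above 30 ms |
|---|---|---|---|
| 4.5 v 2 months | 8 | 5.2% v 3.9% | 2.7% v 1.8% |
| 4.5 v 2 months | 10 | 8.2% v 6.0% | 9.4% v 6.7% |
| 4.5 v 2 months | 12 | 12.0% v 8.8% | 18.3% v 13.4% |
| 8 v 5.6 months | 10 | 10.2% v 8.9% | 12.1% v 10.3% |

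The last row borrows the design's OS medians as a proxy for time on treatment. At a larger SD of 15 ms, with 4.5 v 2 months, rises above 60 ms were 1.7% v 1.1%; absolute values above 500 ms still rounded to zero.

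**4. Concomitant drugs alone.** With equal 4-month medians and s = 10 ms, the rate above 450 ms is about 7.9% with no listed-drug use. In CCR it becomes 8.3% if 10% of subjects use a drug adding 5 ms, and 22.2% if 40% use one adding 20 ms. Usage and effect are both assumed.

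**5. Both together, no AG-221 effect.** With 4.5 v 2 months, s = 10 ms, and 40% of CCR using a drug that adds 10 ms, the rates above 450 ms are 8.3% (AG-221) v 11.0% (CCR). The order reverses relative to step 3.

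**6. A fixed window.** C1D15, C2D1 and C2D15 give k = 3 for every subject who completes two cycles. If each ECG has chance p of being an outlier, 1 − (1 − p)³ is 1.5%, 3.0%, 5.9% and 14.3% for p = 0.5%, 1%, 2% and 5%, the same in both arms.

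**The case against.** The strongest reply is that the SAP already has other views of QTc. SAP 11.7 summarizes ECG values and changes at each time point by group, which avoids the maximum and includes the Cycle 1 and 2 visits. SAP 11.2 gives QT prolongation its own tables, including serious, grade 3 or higher and time to first onset. SAP 11.1 gives several adverse-event tables per person-year. No QTc hypothesis test is planned. All of this stands, and it makes the point one of interpretation. These displays do not correct the category tables, however. The time-point summaries report no outlier categories, cover only subjects still on treatment, and leave the concomitant-drug difference in place.

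A reader might infer that use of the listed drugs appears only in a listing. It does not: SAP 8.4.1 also tabulates concomitant medications by preferred term. What is missing is the link from that use to the QTc categories.

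A reader might also compare 8 ECGs with 2 and conclude that AG-221 would show about three times the CCR rate. That needs every CCR subject to stop after one cycle and every AG-221 subject to complete six. Protocol 7.2.1 states only an aim. Azacitidine, LDAC and BSC are also continuous cycles until End of Trial unless discontinued (Protocol 7.2.2, 7.2.3 and 7.2.5).

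Finally, no document says that CCR subjects do restart the listed drugs. With equal treatment times and no such use, both effects vanish.

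**Conclusion.** The point holds for the lower outlier categories: above 450 ms and rises above 30 ms. A difference there cannot be attributed to AG-221 from the maximum-based tables alone. Under the assumed SDs of 8 to 12 ms and medians of 4.5 v 2 months, the chance gap is roughly 1 to 5 percentage points (2.7% v 1.8% up to 18.3% v 13.4% for rises above 30 ms). It shrinks as treatment times converge.

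It would go too far to say the QTc tables cannot be read at all. At those SDs the ECG-count effect is negligible above 60 ms and above 500 ms, and the time-point and adverse-event displays remain informative. The concomitant-drug effect is possible in any category, but its size is unknown because the documents give no usage figures. Treatment time by arm and QTc variability are likewise not given, so every percentage here is conditional on assumptions. This is an inexpensive improvement to a descriptive safety analysis and does not affect type I error.

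**What to change.** In SAP 11.7:

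1. Add between-arm QTcF and QTcB category tables, for absolute value and for change, restricted to scheduled ECGs through Cycle 2 (C1D15, C2D1, C2D15). Show the number of subjects and of ECGs contributing in each arm.
2. Keep the all-ECG maximum tables as planned.
3. As a labelled sensitivity display only, show the QTc categories by on-treatment use of a QT-prolonging drug listed in Protocol 8.2 (yes/no). State that this conditions on a post-randomization event.

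The cost is SAP wording and a few tables from data already collected. The Cycle 1-2 table misses late changes, which the retained table shows. Subjects who stop in Cycle 1 still contribute fewer ECGs, so the window removes most of the duration effect but not all of it. No change to any concomitant-drug rule is proposed.
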